9.3 Primary Efficacy Analysis Methods

The primary outcome for this study is a binary measure assessed at weeks 4, 8, and 12. A positive response is defined as a decrease from baseline of at least 10 points on the CAPS-5 score (Schnurr et al., 2022) and a reduction of at least 1 risk level of alcohol use, as defined by WHO (Knox et al. 2018). The treatment effect on comorbid PTSD + AUD over time will be assessed using a mixed logistic regression model. The model will be used to generate point and interval estimates of the risk differences and to test differences in proportions of PTSD+AUD resolution between treatment groups at the 8-week visit (primary timepoint), as well as at weeks 4 and 12 (secondary timepoints). The model will include fixed effects for the treatment group, visit (as a categorical variable), gender, site, presence/absence of anti-depressants, treatment-by-visit interaction, and random effects for participant (see model statement below). This approach will provide consistent estimates and valid inferences under missing at random (MAR) data assumptions while accounting for correlation among multiple measures on the same participant. This mixed model will improve the power of the study and the precision of all estimates by allowing all available measures for an individual to be incorporated in the analysis, even if other timepoints are missing. Sensitivity analysis maybe considered by excluding participants that have a low or moderate WHO risk level at baseline. This model is further described below:

$$g(E(Y_{ij})) = \beta_0 + \beta_1 \text{Visit}_{ij} + \beta_2 \text{Site}_{ij} + \beta_3 \text{Treatment}_{ij} + \beta_4 \text{Gender}_{ij} + \beta_5 \text{Anti-depressant}_{ij} + \beta_6 (\text{Treatment} * \text{Visit})_i + s_i + \varepsilon_{ij}$$

Where $g(E(\cdot))$ indicates the identity link function on the expected value of Y , Y_{ij} is the j th measure of PTSD+AUD measurement in subject i , β_0 is the intercept, β_1 through β_6 are coefficients, s_i is a random subject effect and ε_{ij} is the residual error term.

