Statistical analysis modeling will be carried out utilizing SAS/STAT PROC GLIMMIX (SAS Institute Inc. 2017) with the general structure of the SAS code for this model is listed below. Generalized linear mixed models (GLMMs) are a flexible generalization of the linear mixed effect model that allows response outcomes to have an error distribution other than the normal distribution (McCullagh, & Nelder, 1989). The GLMM will employ random intercepts for the between participants' part of the covariance model, and the within participants' part of the covariance model will be initially assumed as autoregressive. The study's primary hypothesis will be tested and associated odds ratio obtained using the 'oddsratio' statement which estimates the risk difference in PSTD+AUD resolution between the treatment arms.

```
proc glimmix data=anlydata;
  class patient treat gender visit site antidepress;
  model primoutcome = treat gender visit site antidepress
    treat*visit/ solution link=logit dist=binary oddsratio;
    random int / type=ar(1) subject=patient;
    ods select parameterestimates Oddsratios;
run;
```

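### SAP 9.3 names no estimation method for the primary mixed logistic model, and the software default does not estimate the odds ratio consistently with at most three binary records per participant

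*SAP*

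**What the plan says.** SAP 9.3 defines the outcome and its visits: "The primary outcome for this study is a binary measure assessed at weeks 4, 8, and 12". Each participant therefore contributes at most three binary records. The text describes a mixed logistic regression with a random participant effect and states: "This approach will provide consistent estimates and valid inferences under missing at random (MAR) data assumptions".

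The code opens "proc glimmix data=anlydata", continues "model primoutcome = treat gender visit site antidepress" and "treat*visit/ solution link=logit dist=binary oddsratio", and adds "random int / type=ar(1) subject=patient". It has no METHOD= option and no EVENT= option. It is introduced "with the general structure of the SAS code for this model is listed below", so it is not offered as final code, but no other part of the SAP or protocol supplies an estimation method. The text also says that "the within participants' part of the covariance model will be initially assumed as autoregressive".

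SAP 9.3 speaks of risk differences, but the only output the code selects is parameter estimates and odds ratios.

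**The concern.** When METHOD= is absent and the model has a random effect, PROC GLIMMIX fits residual pseudo-likelihood. It linearises the model and applies REML to pseudo-data. That is not the likelihood of the binary data, so the argument that a likelihood analysis may ignore MAR missingness does not carry over. With few binary records per person, linearisation also shrinks both the random-intercept variance and the subject-specific log odds ratio, even when the data are complete.

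This model carries the only formal primary test (SAP 7.7), and SAP 9.3 ties that test to the odds ratio. At stake are the reported odds ratio, its confidence interval and some power.

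A smaller default sits in the same call. Without EVENT=, the procedure models the first ordered level of the outcome. Under 0/1 or No/Yes coding, the printed odds ratio would be for non-response.

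**Working it through.** **Inputs from the documents.** 45 per arm, 5/45 (11%) versus 17/45 (38%), two-sided 0.05, about 30% attrition (SAP 6; Protocol 10.5). Binary outcome at three visits; terms for treatment, visit, treatment by visit, gender, site and antidepressants; random intercept (SAP 9.3).

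**Assumed.** The default estimator, and a random-intercept SD of 1, 2 or 3 on the logit scale. The within-person correlation on the latent scale is SD²/(SD² + π²/3): 1/4.29 = 0.23, 4/7.29 = 0.55, 9/12.29 = 0.73.

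**Step 1: the plan's own power.** Arcsine approximation with continuity correction 1/(2n) = 1/90:

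Φ(2[asin√(p₂ − 1/90) − asin√(p₁ + 1/90)]·√(45/2) − 1.96)

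For 5/45 versus 17/45: Φ(2[asin√0.3667 − asin√0.1222] × 4.743 − 1.96) = Φ(0.82) = 0.795. For 5/45 versus 14/45 it gives 0.560. Both match the table in Protocol 10.5. That calculation is for Fisher's exact test and is not affected by this point.

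**Step 2: the target.** With the Week 8 response rates held at 11.1% and 37.8% after averaging over the random intercept, the true subject-specific log odds ratio is 1.832, 2.430 and 3.176 at SD 1, 2 and 3. The population-averaged value is ln[(17/28)/(5/40)] = ln 4.857 = 1.58 throughout.

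**Step 3: 45 per arm, 2,000 simulated trials per row.** Each data set was fitted by residual pseudo-likelihood (PL, scale fixed at 1) and by maximum likelihood with 31-point quadrature (ML). Bias = (mean − true)/true. In the dropout rows about 30% are lost by Week 12, MAR, with non-responders more likely to leave.

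| Setting | True | PL mean (bias) | PL coverage | PL power | ML mean (bias) | ML coverage | ML power |
|---|---|---|---|---|---|---|---|
| 11% v 38%, SD 1 | 1.832 | 1.739 (−5%) | 95% | 81% | 1.967 (+7%) | 96% | 84% |
| 11% v 38%, SD 2 | 2.430 | 1.849 (−24%) | 82% | 76% | 2.635 (+8%) | 96% | 83% |
| 11% v 38%, SD 3 | 3.176 | 1.996 (−37%) | 61% | 74% | 3.667 (+15%) | 96% | 80% |
| 11% v 38%, SD 2, dropout | 2.430 | 1.966 (−19%) | 86% | 69% | 2.767 (+14%) | 97% | 76% |
| 11% v 31%, SD 2, dropout | 1.951 | 1.611 (−17%) | 89% | 47% | 2.257 (+16%) | 96% | 54% |

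Without dropout, the median estimated intercept variance under PL is 0.65 (true 1), 1.70 (true 4) and 2.66 (true 9). Under ML it is 0.91, 3.88 and 9.20.

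**Step 4: consistency.** At 1,000 per arm, SD 2, complete data (300 trials), PL averages 1.692 against 2.430 (−30%, coverage 0%). ML averages 2.445 (+1%, coverage 96%). The PL bias does not vanish with sample size, and no missing data are needed to produce it.

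**Step 5: no treatment effect.** Rejection at nominal 5%, PL versus ML:
- 20% response, SD 2, no dropout: 3.3% v 5.0%
- 20% response, SD 2, dropout: 3.2% v 4.3%
- 25% response, SD 3, dropout: 3.0% v 4.9%
- 11% response, SD 2, dropout: 1.2% v 1.9%

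**Step 6: population-averaged risk difference.** True 0.267. PL gives 0.258, 0.250 and 0.247 at SD 1, 2 and 3, so the largest shortfall is (0.267 − 0.247)/0.267 = 7%. ML gives 0.266 to 0.269.

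**Step 7: other settings.** With visit-specific rates (placebo 8/11/13%, active 25/38/40%) and about 10/21/30% missing at random, PL averages 1.69 against 1.83 at SD 1 (−8%, coverage 94%) and 1.74 against 2.43 at SD 2 (−28%, coverage 84%). A further run at 11% versus 38% gives attenuation of about 10/30/43% and coverage of 95/80/53% at SD 1/2/3. Across all runs the power loss against quadrature is about 3 to 8 points.

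**The case against.** The strongest reply is that the confirmatory test survives. A reader might infer from the failed consistency claim that the primary test is invalid or has an inflated false-positive rate. The documents and the calculations do not support that: the null hypothesis is the same on every scale, and rejection under it stays below 5% throughout. That part of the objection stands.

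Second, the large figures need a large SD, and no document gives one. At SD 1 the default covers at 95% and is no more biased in size than quadrature (−5% against +7%). The pseudo-likelihood mean itself moves little (1.74 to 2.00 without dropout). The gap widens mainly because the subject-specific target grows with the SD. Against the population-averaged 1.58 the default is not attenuated at all. This stands as a limit on size. It does not rescue the claim, because the fitted model is subject-specific and the code prints its odds ratio.

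Third, SAP 9.3 names risk differences, and on that scale the effect is small. That also stands, but the listed code produces no risk difference.

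Fourth, the code is only a general structure. True, but nothing else in either document fills the gap, so the method is either the default or an unrecorded later choice.

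Fifth, a reader might infer that the printed odds ratio will certainly be for non-response. The coding of the outcome is not stated, so this cannot be concluded. The p-value is the same either way.

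Finally, the simulations used purpose-written fits, not SAS. They did not include the high-dose arm (SAP 7.1), the site with one participant (SAP 7.6) or a residual AR(1) term.

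**Conclusion.** The concern holds for the odds ratio and its interval. As coded, the primary model would be fitted by a method that is not consistent for its own odds ratio, contrary to the SAP's statement. At the planned size, attenuation is about 5-10% with about 95% coverage at SD 1, about 20-30% with 80-86% coverage at SD 2, and about 40% with 50-60% coverage at SD 3. Power is about 3-8 points lower than with quadrature.

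This rests on two assumptions that the documents do not settle: the software default, and the between-participant SD. No single attenuation figure can be quoted without the SD. Because the test keeps its level and the risk difference is little affected, this is a should-fix and not a reason to doubt the validity of the primary test.

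**What to change.** In the SAP 9.3 code:
- Add `method=quad(qpoints=15)` to the procedure statement, with Laplace as the stated fallback if quadrature does not converge.
- Keep the random intercept by participant as the only random term and drop `type=ar(1)`. On a single intercept the covariance matrix is 1×1, so the option does nothing.
- Set `event=` on the response to the responder level, so that the odds ratio is for response whatever the coding.

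In the SAP 9.3 text:
- Name the estimation method.
- Delete the sentence that assumes an autoregressive within-participant structure. Quadrature and Laplace cannot fit a residual AR(1). If that structure is wanted, the model would have to be made marginal instead.

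The cost is a few code options, a short text edit and a slightly longer run time. Statistically, the quadrature odds ratio has a modest upward small-sample bias (roughly 2-16% across the simulations), and residual AR(1) is given up. In return, coverage is 96-97% in the 45-per-arm runs tabulated, and the MAR statement matches what is fitted. Protocol 10.1 has the SAP finalised before data lock and unmasking, so the change belongs before that point.

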9.3.1 CAPS

As mentioned above, the CAPS-5 is a continuous measure that is assessed at baseline and weeks 4, 8, and 12. The CAPS-5 Total Symptom Severity Score ranges from 0 to 80, with higher scores indicating greater PTSD symptoms (Weathers et al., 2018). The treatment effect on the clinical criteria of PTSD as measured by the CAPS-5 over time will be

assessed using a generalized-linear mixed model to account for temporal correlation between measurements and the clustering of the data. This model will include fixed effects for treatment group, visit (as a categorical variable), gender, site, presence/absence of anti-depressants, and a treatment-by-visit interaction term, and a random effect for participant (see model statement below).

$$Y_{ij} = \beta_0 + \beta_1 Visit_{ij} + \beta_2 Site_{ij} + \beta_3 Treatment_{ij} + \beta_4 Gender_{ij} + \beta_5 Anti-depressant_{ij} + \beta_6 (Treatment * Visit)_i + s_i + \varepsilon_{ij}$$

Where Y_{ij} is the j th measure of CAPS-5 in subject i , β_0 is the intercept, β_1 through β_6 are coefficients, s_i is a random subject effect and ε_{ij} is the residual error term.

Statistical analysis modeling will be carried out utilizing SAS/STAT PROC MIXED (Littell, Milliken, Stroup, Wolfinger, & Schabenberger, 2006) with the general structure of the SAS code for this model shown below. Adjusted marginal means (also called LS means) will be used to report and test for differences in mean change in CAPS-5 score at 8 weeks for the placebo and BUP/NTRX groups, providing 95% confidence intervals and a p-value for the difference between them.

```
proc mixed data = anlydata;
  class patient treat gender visit site antidepress;
  model CAPS5_Score = treat gender visit site antidepress
    treat*visit /s;
  random int / subject= patient;
  repeated visit / type=cs subject= patient;
  lsmeans treat*visit;
run;
```

9.3.2 %HDD

As mentioned above, %HDD is assessed by the TLFB and is collected at baseline and weeks 2, 4, 6, 8, 10, and 12. The treatment effect on the clinical criteria of AUD as measured by %HDD over time will be assessed using a generalized-linear mixed model to account for temporal correlation between measurements and the clustering of the data. A similar model to that listed in Section 9.3.1 will be run to produce adjusted marginal means to report and test for differences in mean %HDD for the placebo and BUP/NTRX groups, providing 95% confidence intervals and a p-value for the difference between them. NOTE: the lookback period to derive %HDD will be performed at 28-days, each derived measure at a specific timepoint based on the baseline visit date. Sensitivity analysis maybe also performed using a 14-day look-back period.

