4.3 Study Arm Assignment and Randomization

At baseline, participants who meet eligibility criteria are randomized to treatment A (buprenorphine 2mg SL with naltrexone 380mg IM) or treatment B (SL placebo and IM placebo). The treatment allocation ratio for the treatment vs. placebo regimens is 1:1 and is stratified by site, presence of concomitant antidepressants, and gender using a random permuted block scheme with variable block size. The randomization schedule is created by the PASA statistician who coordinates with the local research pharmacies and develops the web-based randomization assignment system. At week 8, the participants will remain on the assigned treatment and dose from week 8 to 12.

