6 SAMPLE SIZE DETERMINATION

The sample size for a proof-of-concept study should be large enough to be able to detect a drug effect or surrogate signal, but at the same time expose a minimum number of subjects to an experimental drug combination in a reasonable timeframe within a restricted budget. Sample size was determined based on sample sizes used in similar double-blind, placebo-controlled studies of PTSD and AUD, and based on the estimated recruitment rate over the allotted enrollment timeline. With these factors in mind, we plan to enroll approximately 180 participants to allow screen failures/drop-out prior to randomization of approximately 90 participants across three sites (45 in each treatment arm) within a 24-month enrollment period. We estimate that attrition will be approximately 30%. However, all randomized participants will remain in analysis (intent-to-treat) regardless of how long they participate in the study.

For the primary outcome, we assumed the following success rates based on a similar previous study: Placebo arm 5/45 (11%) or less and 2mg BUP/NLTRX arm 17/45 (38%) or greater. We calculated power for two by two contingency tables for comparison of the treatment and Placebo arm using a Fisher's Exact test with the Walters approximation applying a nominal two-sided alpha level of 0.05. We observe power of 80% or greater for the above assumptions. In addition, a situation with more positive responses in the active treatment arm or fewer positive responses in the placebo arm would increase apparent power.

For secondary outcomes, we estimate that we will have >80% power to detect a medium effect size (Cohen's $f=0.25$, two-sided alpha level of 0.05) at 8 weeks. Under optimal conditions, where the correlation between consecutive observations on the same participant is high, and the variability observed between pairs of time points is fairly constant, fewer participants would be required (see table below). Under a less than ideal, worst-case situation where correlation between measurements is low and the variability observed between pairs of time points changes, the proposed sample size is still large enough to detect a moderate effect size, even after accounting for screen failures and drop-outs.

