For the Psychophysiological and Fear Conditioning analyses, a total sample size of 90 (45 per group) will allow for a conservative dataset with over 80% power to detect significant differences between the treatment group against the placebo group at the $\alpha = 0.05$ level. Estimates were based on means and standard deviations from previous study samples.

Estimated Sample Sizes per Group for Detecting a Moderate Effect Size at 80% Power			
Modeling Conditions	AUD Outcome	PTSD Outcome	Higher of PTSD/AUD with Screen Failures and Drop-outs (+15)
High Correlation, Constant Variance	42	30	57
High Correlation, Non-constant Variance	42	63	78
Low Correlation, Constant Variance	81	57	96
Low-Correlation, Non-constant Variance	81	120	135

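### The CAPS-5 mixed model, reused for the other continuous outcomes, enters one variance component twice and forces compound symmetry, so Week 8 standard errors can be wrong in either direction

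*SAP*

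**What the plan says.** SAP 9.3.1 fits the CAPS-5 score, measured at baseline and Weeks 4, 8 and 12, with visit as a class variable and no baseline covariate. The code has a random intercept, "random int / subject= patient", and a compound-symmetric residual, "repeated visit / type=cs subject= patient". Its LSMEANS statement requests treatment-by-visit means, while the text promises a test of the treatment difference in mean change at Week 8.

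For %HDD, SAP 9.3.2 states: "A similar model to that listed in Section 9.3.1 will be run". SAP 9.4.1 to 9.4.4 say the same for PCL-5, PHQ-9, VR-12 and PEth. For these models neither document names an unstructured covariance, an empirical (sandwich) standard error, a degrees-of-freedom method or a fallback structure.

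Three other places bear on this:

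- The text of SAP 9.3 starts from an autoregressive within-participant covariance for the composite, which is built partly from the same CAPS-5 scores.
- SAP 6 plans for a "worst-case situation where correlation between measurements is low and the variability observed between pairs of time points changes". Its table raises the PTSD size per group from 30 to 63 (high correlation) or from 57 to 120 (low correlation) when variance is not constant. The AUD sizes do not move (42 and 42; 81 and 81).
- SAP 9.2 lists CAPS-5 and %HDD under primary outcomes, and SAP 9.1 says PTSD and AUD differences will be formally tested. SAP 7.7 reserves the one formal 0.05 test for the composite at Week 8.

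**The concern.** There are two separate defects.

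First, a random intercept and a compound-symmetric residual for the same participant are the same component. The fit cannot separate them. Possible consequences are convergence or non-positive-definite warnings and a change in the default degrees of freedom.

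Second, compound symmetry with model-based standard errors replaces the Week 8 variance by an average over visits (for a difference in level) or over pairs of visits (for a difference in change). If variances or correlations differ by visit, the Week 8 interval and p-value are miscalibrated. At stake are the two component analyses, which SAP 7.7 gives no share of the formal 5% but SAP 9.1 calls formal, and every exploratory continuous outcome.

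**Working it through.** **Inputs from the documents.** Level: "two-sided alpha level of 0.05) at 8 weeks" (SAP 6). Size: 45 per arm (SAP 6). Allocation: "The treatment allocation ratio for the treatment vs. placebo regimens is 1:1" (SAP 4.3). Attrition: about 30% (SAP 6). CAPS-5 visits: baseline and Weeks 4, 8, 12 (SAP 9.3.1).

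**Inputs not in the documents.** Visit-specific SDs and correlations are not given. Everything below that uses them is an assumption, shown over a range.

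**The plan's own figures.** Only the last column of the SAP 6 table can be checked: 42+15=57, 63+15=78, 81+15=96, 120+15=135. The rest cannot be rebuilt without its correlations and variances.

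**Identifiability.** Let a be the random-intercept variance, b the CS covariance and s the residual. The implied variance is a+b+s and the implied covariance is a+b. Only a+b is estimable. The marginal model is still plain compound symmetry, so the duplication does not itself shrink the standard error.

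**What compound symmetry does with complete data.**

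- Level at Week 8: SE ratio (model to true) = sqrt(average visit variance / Week 8 variance).
- Change to Week 8: SE ratio = sqrt(average variance of all pairwise differences / variance of the baseline-to-Week-8 difference).
- Approximate type I error = 2(1−Φ(1.96 × ratio)).

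**Change, constant variance, AR(1) with ρ per 4 weeks.** In units of 2σ², the average pairwise value is 1−(3ρ+2ρ²+ρ³)/6 and the true value is 1−ρ². The shortfall is ρ(1−ρ)(3−ρ)/6, which is positive for every ρ between 0 and 1. At ρ=0.7: 0.4295/0.51=0.842, SE ratio 0.918, type I error 7.2%. At ρ=0.3, 0.5 and 0.85 it is 6.4%, 6.9% and 7.3%.

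**Narrow baseline, SDs 7/11/11/11, correlation 0.5.** Pairs with baseline: 49+121−77=93. Other pairs: 121. Average: (3×93+3×121)/6=107. SE ratio for change = sqrt(107/93)=1.07, so type I error is about 3.5%: conservative.

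**Level.** Rising SDs 7/10/12/13: sqrt(115.5/144)=0.90, too small. Falling SDs 13/11/9/8: sqrt(108.75/81)=1.16, too large.

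**%HDD by construction.** With 28-day windows at baseline and Weeks 2 to 12, adjacent windows share 14 days and all others share none. Assume exchangeable daily drinking and full windows. The difference variance for adjacent windows is then half that of the others. Of 21 pairs, 6 are adjacent: (15+6×0.5)/21=0.857, SE ratio 0.926, about 7.0% for change. Overlap alone leaves the visit variances equal, so it does not distort the level contrast with complete data.

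**Null simulation.** 1,500 trials per scenario, 90 participants, REML fit of the marginal model. Each range covers 0% and 30% non-informative dropout. Monte Carlo error is about 0.6 points at 5%.

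| Assumed SDs; correlation | Rejection, level | Rejection, change |
|---|---|---|
| 10/10/10/10; CS 0.5 | 3.7%–5.0% | 5.1%–5.5% |
| 10/10/10/10; AR 0.7 | 5.1%–5.5% | 7.9%–8.7% |
| 7/10/12/13; AR 0.7 | 8.1%–8.9% | 5.9%–7.2% |
| 8/10/11/12; CS 0.5 | 6.6% | 3.7%–4.3% |
| 7/11/11/11; CS 0.5 | 6.9%–7.3% | 3.5%–4.7% |
| 13/11/9/8; CS 0.5 | 1.8%–2.3% | 5.5%–7.5% |
| 13/11/9/8; AR 0.7 | 2.3%–2.8% | 8.1%–10.3% |
| 8/10/10/15; CS 0.5 | 3.0%–3.9% | 1.6%–1.8% |

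With seven visits and AR 0.85 between adjacent visits, level ran from 2.7% to 8.7% and change from 6.3% to 14.3%. Over all scenarios the model SE was between 25% too small and 25% too large. Without the CS restriction, rejection was near 5% throughout: 4.1% to 6.7% with a cluster sandwich SE, and 3.9% to 6.9% with a visit-specific t-test.

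**The case against.** The strongest reply is that no direction of error is established and that the affected analyses do not carry the trial's formal conclusion. Both parts stand. The documents give no visit SDs or correlations, several plausible patterns make the test conservative, and SAP 3.2.1 presents CAPS-5 and %HDD as complements to a composite that is fitted by a different model.

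Stronger readings are tempting, but the documents do not support them:

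- A reader might infer that the CAPS-5 entry threshold of 26 narrows the baseline spread and so makes the Week 8 test of change too liberal. With a narrow baseline and equal correlations the change test is conservative (107 against 93 above). Only the level contrast becomes liberal.
- A reader might take the table's ratio of about 2.1 (63/30, 120/57) as the factor by which the fitted variance is too small, which would give 2(1−Φ(1.96/√2.1)), about 18%. Those are planned sample sizes under unstated inputs. The fitted model estimates its variance from trial data, so the ratio says nothing about its calibration.
- A reader might extend the planning scenario to every outcome. It moves only the PTSD column, and the SAP calls its most extreme row a worst case. For %HDD the argument rests on the overlapping windows. The optional 14-day look-back in SAP 9.3.2 would remove that overlap, but only in a sensitivity analysis.

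None of this answers the duplicated component, the restrictive structure without a robust standard error, or the mismatch with SAP 9.3.

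**Conclusion.** The specification is wrong as written. One component is entered twice and is not identifiable. Compound symmetry is imposed with model-based standard errors, although the SAP assumes autoregression for a related outcome and allows changing variance for PTSD.

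The Week 8 standard errors can err either way. Type I error ran from about 2% to 10% in the four-visit simulations, under assumed SDs and correlations and non-informative dropout. Bias under outcome-dependent dropout was not measured. One direction is firm, but conditional: for change from baseline with constant variance and decaying correlation the test is anti-conservative, at about 6% to 9%.

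A reader might infer that the trial's 5% error rate is breached. It is not, because the composite test in SAP 7.7 does not use this model. The CAPS-5 and %HDD component tests and the exploratory outcomes are affected, and their code should be corrected before unmasking.

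**What to change.** 1. Delete the RANDOM statement in SAP 9.3.1. Use `repeated visit / type=un subject=patient` and add `ddfm=kr` to the MODEL statement. As coded, with baseline as a response, CAPS-5 then has 4×5/2=10 covariance parameters. It would have 3×4/2=6 only if baseline were moved to a covariate, which changes the model and should be a deliberate choice.
2. For %HDD (7 visits, 28 parameters) and PCL-5 (8 visits, 36 parameters), fix a fallback order to be used only if the unstructured fit fails: heterogeneous Toeplitz, then heterogeneous AR(1). Use empirical standard errors for any structured fallback and name a degrees-of-freedom rule for it, because Kenward-Roger adjusts the model-based variance.
3. Write the Week 8 treatment contrast into the code for each outcome, and say whether it is a difference in level or in change. Text, code and the tables listed in SAP Appendix B should then agree.

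The cost is a few lines of SAP text and code, some extra covariance parameters and possibly slightly wider intervals. No data collection changes.

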7 STATISTICAL / ANALYTICAL ISSUES

7.1 General Rules

All statistical computations will be performed and data summaries will be created using SAS 9.4 or higher. If additional statistical packages are required, these will be discussed in the study report. For summaries of study data, categorical measures will be summarized in tables listing the frequency and the percentage of participants; continuous data will be summarized by presenting mean, standard deviation, median and range; and ordinal data will be summarized by only presenting median and range. Model-based analyses described in Section 9 will be used to obtain point estimates and associated confidence intervals for various measures as well as p-values for comparisons of data between treatment groups. Note: initial models will include the high dose treatment arm; however, if the model cannot converge due to the small number of participants randomized to this arm prior to removal from the study, then the model will only compare outcomes between the low dose and placebo treatments. P-values presented will be based on two-sided tests unless otherwise specified and generally only adjusted for randomization factors (study site, gender, and presence of concomitant antidepressants). Note: in the event a model cannot converge due to small sample sizes for a specific randomization factor, it will be removed from the model. For continuous outcomes, checks of normality will be performed and if required, transformations or non-parametric tests will be employed.

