7.6 Multicenter Studies

This is a 3-center study including Tuscaloosa Research & Education Advancement Corporation (TREAC)/Tuscaloosa VA Medical Center (TVAMC), Connecticut Research & Education Foundation (CREEF)/VA Connecticut Healthcare System (VACT), and Wayne State University. Although we initially expected the total number of enrolled participants to be roughly equal across the three study sites, only one participant from the Wayne State site enrolled and completed the study. Since randomization was stratified based on study site, site will be included as a term in all model-based analyses. Since only one participant was enrolled at Wayne State, this participant will be removed during sensitivity analyses so comparisons can be made between study site.

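### The printed CAPS-5 LS means weight the three sites equally, so the single Wayne State participant carries one third of each absolute arm-by-visit mean; treatment differences are unaffected.

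*SAP*

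**What the plan says.** The CAPS-5 code in SAP 9.3.1 declares "class patient treat gender visit site antidepress" as class variables. It enters treatment, gender, visit, site and antidepressant use as fixed effects with a treatment-by-visit interaction, and ends with "lsmeans treat*visit". There is no treatment-by-site term and no weighting option. The text says "Adjusted marginal means (also called LS means) will be used to report and test for differences in mean change", with 95% intervals and a p-value for the difference between arms. Sections 9.3.2 and 9.4.1 to 9.4.4 apply a similar model to %HDD, PCL-5, PHQ-9, VR-12 and PEth.

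On sites, SAP 7.6 begins "This is a 3-center study including", then reports that "only one participant from the Wayne State site enrolled and completed the study" and that "site will be included as a term in all model-based analyses". Of the Wayne State participant it says "this participant will be removed during sensitivity analyses so comparisons can be made between study site". SAP 7.1 adds that "in the event a model cannot converge due to small sample sizes for a specific randomization factor, it will be removed from the model".

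Neither document says how LS means are to be weighted over site, gender or antidepressant use.

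**The concern.** An LS mean from an additive model is a prediction averaged over the other factors. By default SAS gives each level of a class factor the same weight, however many participants it holds. With two well-filled sites this would be harmless. With a third site of one person, a third of the average rests on a site effect estimated from that person alone.

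Two provisions might have caught this, and neither corrects the main fit. The rule in 7.1 acts only on non-convergence, and a linear mixed model with a one-person site can normally be fitted. The removal in 7.6 is confined to sensitivity analyses and is meant to allow site comparisons.

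At stake is whether the adjusted level of CAPS-5, %HDD and the other scores in each arm describes the enrolled participants, and whether the intervals around those levels are of sensible width. A reader who sees a wide interval for each arm beside a narrower one for their difference could easily misread both.

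**Working it through.** The documents give no LS-mean standard error, so there is no figure of theirs to reproduce.

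**Inputs from the documents.** Three site levels and one Wayne State participant (SAP 7.6); about 90 randomised, 45 per arm, and 30% attrition (SAP 6); four CAPS-5 assessments and a compound-symmetry structure (SAP 9.3.1).

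**Assumed inputs.** Within-participant correlation ρ of 0.3 to 0.7; 10 to 50% women; half on antidepressants; the other two sites equal in size. Total variance is set to 1, so standard errors are in SD units.

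**Weight.** The default coefficient for each site is 1/3. In the generalised least squares solution the coefficients on the single participant's data sum to 1/3 in each arm-by-visit mean. This holds in both arms, including the one the participant was not in. With observed margins the sum is 1/90 = 0.011.

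**Standard error, approximate by hand.** The participant's four-visit average has variance ρ + (1 − ρ)/4. With weight 1/3 it adds one ninth of that to the variance of an arm mean, about 1/45:

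SE ≈ √[1/45 + (1/9)(ρ + (1 − ρ)/4)], compared with √(1/45) = 0.149.

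| ρ | ρ + (1 − ρ)/4 | SE, equal weights | Ratio to 0.149 |
|---|---|---|---|
| 0.3 | 0.475 | √(0.0222 + 0.0528) = 0.274 | 1.84 |
| 0.5 | 0.625 | √(0.0222 + 0.0694) = 0.303 | 2.03 |
| 0.7 | 0.775 | √(0.0222 + 0.0861) = 0.329 | 2.21 |

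**Standard error, full model.** At ρ = 0.5 with 20% women and no dropout, the Week 8 SE is 0.30 in the participant's arm and 0.32 in the other. Observed margins give 0.15, and a two-site fit gives 0.16. Over the whole assumed range at 45 per arm, with and without 30% attrition, the ratio in the participant's arm is 1.66 to 2.29 against observed margins and 1.50 to 2.09 against the two-site fit. It is slightly higher in the other arm. At 30 per arm the ratios are about 1.3 to 2.1.

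**Shift.** If the participant's average lay, say, 15 points from what the model would otherwise expect, both arm means would move by about 15/3 = 5 points, against 15/90 = 0.17 with observed margins. The 15 is purely illustrative.

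**What cancels.** Site enters additively, so it drops out of the difference between arms at a visit and out of Week 8 minus baseline within an arm. The participant's summed weight is 0 in both. The SE of the between-arm difference is 0.213 with or without the participant. The SE of the within-arm change is 0.149 with the participant and 0.151 without.

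**Where it does not cancel.** SAP 9.3 plans risk differences, and its code uses a logit link. Take the planning rates, 5/45 and 17/45, as holding at the two main sites. The logits are ln(5/40) = −2.079 and ln(17/28) = −0.499, and the difference in proportions is 0.378 − 0.111 = 0.267. Suppose the Wayne State site effect were +1 on the logit scale. Equal weighting adds 1/3 to both logits, giving 0.459 − 0.149 = 0.310. With −1 it gives 0.303 − 0.082 = 0.221. The odds ratio is unchanged, but the risk difference is not. The ±1 is an illustration only, with the random intercept held at zero.

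**The case against.** The strongest reply is that the distorted quantity is not one the SAP undertakes to report. Section 9.3.1 names differences in mean change, with an interval for the difference. Appendix B lists tables comparing change and plots of mean change from baseline, and no table or figure of absolute arm levels. This stands. A reader might infer that one participant sways every reported arm mean, or the treatment effect itself. The documents do not support that: there is no treatment-by-site term, and the coded response is the score itself, with baseline listed among the assessments, so site cancels from both contrasts. It would re-enter the arm mean changes, though not their difference, if change scores were made the response.

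A second reply is that SAP 9.3.1 presents the code only as a general structure. It lacks the options needed for the promised tests and intervals, so the missing weighting option need not be a settled choice. That is fair, and it is also the reason to settle the choice now. As printed, arm-by-visit levels are the only LS-mean output.

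Third, the sensitivity fit without the participant would expose any distortion. It would, but no rule says which set of arm means is then to be reported.

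Finally, the size rests on assumed values, and equal weighting is a common convention. Both are true. Equal weights for women and men are a matter of preference; a one-third weight for one person is harder to defend.

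**Conclusion.** The point holds as a matter of reporting. Under the printed statement, one participant has weight 1/3 in each absolute arm-by-visit LS mean. That weight follows from the design and needs no assumption beyond the software default. The standard-error inflation of roughly 1.5 to 2.3 times does need assumptions: about 45 per arm, correlation 0.3 to 0.7, and either observed margins or a two-site fit as the comparison. To say flatly that the standard error doubles would go beyond what the documents can support.

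The treatment tests, differences and p-values for the continuous outcomes are not affected, nor is change from baseline taken as a visit contrast.

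For the primary outcome, the odds ratio is free of the weighting. The planned response proportions and risk difference would depend on it if they were obtained from equal-weight LS means under the coded logit link. The SAP does not say how they will be obtained: the printed code has no LS-means statement, and the model statement beside it names an identity link, under which site would cancel from the risk difference. The change is worth making because it costs almost nothing and fixes the weighting before results are seen.

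**What to change.** In SAP 9.3.1, replace the LS-means line with `lsmeans treat*visit / om diff cl`, and state that the same option applies in 9.3.2 and 9.4.1 to 9.4.4. Alternatively, state that arm means are taken from the fit restricted to the two main sites. Specify that change from baseline is a contrast of visits within this model.

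In SAP 9.3, state that Week 8 response proportions and the risk difference are obtained by averaging predicted probabilities over the enrolled sample under each arm, not from equal-weight LS means, and say how the random intercept is treated.

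The cost is one SAS option, a short standardisation step for the primary outcome and a few sentences of text. No data change, and the treatment comparison for the continuous outcomes is essentially unchanged. Make the change before database lock and unmasking.
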